7.7 Prior and Concomitant Medication

Medications (product name) will be coded using the World Health Organization (WHO) Drug Dictionary Global Drug Reference: 2024 Mar version (or more recent version), using the following Anatomical Therapeutic Chemical (ATC) classification codes:

- Product name
- Preferred name
- Drug code
- Anatomical Main Group (ATC 1st level code)
- Therapeutic subgroup (ATC 2nd level code)

- Pharmacological Subgroup (ATC 3rd level name and code)
- Chemical subgroup (ATC 4th level code)

Prior medications are defined as medications that start and stop prior to the first dose of IMP. All other medications will be defined as concomitant medications, including those that start prior to the first dose of IMP and continue thereafter. Any medications with an unknown start or stop date will be assumed to be concomitant medications, unless a partial start or stop date indicates otherwise.

All medications, including coded terms (product name, preferred term ATC 2nd level and ATC 4th level code), will be listed. One combined data listing of prior and concomitant medications will be provided. All prior medications as defined above will be flagged with a "#" symbol. Within this flagged group, medications that started after screening and stopped before dosing of IMP will also be flagged using a "*" symbol.

7.8 Other Baseline Characteristics

All other baseline characteristics, as listed below, at screening and on admission (unless otherwise stated) for each period (as appropriate) will be listed:

- Urine drug screen
- Alcohol breath test
- Carbon monoxide test
- Virology (screening only)
- Serum pregnancy test for female subjects (screening only)
- Urine pregnancy test for female subjects (admission only)
- Follicle stimulating hormone for post-menopausal female subjects (screening only)

8 Efficacy

Not applicable.

9 Pharmacokinetics

9.1 Plasma PK Parameter Estimation

The PK parameters for delafloxacin in plasma will be estimated where possible and appropriate for each subject profile (i.e., regimen) by non-compartmental analysis methods using Phoenix WinNonlin software (v8.3 or a more recent version, Certara USA, Inc., USA). Additional parameters may be calculated if required, depending on the data.

9.1.1 Definition of Plasma PK Parameters

Plasma PK parameter definitions are provided in [Table 2](#).

Table 2 Plasma PK Parameter Definitions and Rounding Specifications

Parameter	Definition	Unit	DP or SF	No. of DP/SF
Tlag	Time prior to the first measurable concentration	h	DP	2
Tmax	Time of maximum observed concentration	h	DP	2
Cmax	Maximum observed concentration	mass unit/mL	SF	3

Parameter	Definition	Unit	DP or SF	No. of DP/SF
AUC(0-24)	Area under the curve from time 0 to 24 h post dose	mass unit.h/mL	SF	3
AUC(0-last)	Area under the curve from time 0 to the time of last measurable concentration	mass unit.h/mL	SF	3
AUC(0-inf)	Area under the curve from time 0 extrapolated to infinity	mass unit.h/mL	SF	3
AUCextrap	Area under the curve from time of the last measurable concentration to infinity as a percentage of the area under the curve extrapolated to infinity	%	DP	2
T1/2	Terminal elimination half-life	h	DP	2
Lambda-z	First order rate constant associated with the terminal (log-linear) portion of the curve	1/h	DP	4
CL/F	Total body clearance calculated after a single extravascular administration where F (fraction of dose bioavailable) is unknown.	mL/min	SF	3
Vz/F	Apparent volume of distribution based on the terminal phase calculated using AUC(0-inf) after a single extravascular administration where F (fraction of dose bioavailable) is unknown	L	SF	3
MRT(0-last)	Mean residence time from time 0 to time of the last measurable concentration	h	DP	2
MRT(0-inf)	Mean residence time extrapolated to infinity	h	DP	2
Frel Cmax	Relative bioavailability based on Cmax	%	DP	2
Frel AUC(0-last)	Relative bioavailability based on AUC(0-last)	%	DP	2
Frel AUC(0-inf)	Relative bioavailability based on AUC(0-inf)	%	DP	2
lambda-z lower*	Lower limit on time for values to be included in the calculation of lambda-z	h	DP	2
lambda-z upper*	Upper limit on time for values to be included in the calculation of lambda-z	h	DP	2

DP = decimal places; NA = not applicable; SF = significant figures

* = these values should be listed but omitted from the descriptive statistics

If 2 dose levels are administered of the same formulation in the same prandial state, then dose-normalised PK parameters will be calculated for the assessment of dose proportionality.

Dose will be used in the calculation of relevant PK parameters as per [Table 3](#).

Table 3 Dose Specifications

Dose (nominal/actual)	Nominal
Precision	As per protocol

Non-dose corrected relative bioavailability (Frel) will be calculated as follows:

$$Frel = \left\{ \frac{AUC \text{ or } Cmax \text{ (test)}}{AUC \text{ or } Cmax \text{ (reference)}} \right\} \times 100$$

Frel will be calculated using Cmax, AUC(0-last) and AUC(0-inf). If for any reason the AUC(0-inf) is not calculable then an alternative or additional AUC over a partial area may be used to calculate Frel for all subjects.

The following comparisons will be made:

- 450 mg delafloxacin Powder for Oral Suspension (test) vs delafloxacin Tablet (reference) (Regimen A)
- 450 mg delafloxacin Powder for Oral Suspension fed (test) vs delafloxacin Powder for Oral Suspension fasted (reference)

9.1.2 Rules for Plasma PK Parameter Estimation using WinNonlin

The imputation of non-numerical (e.g., below the limit of quantification [BLQ]) or negative values (e.g., pre-dose sampling times) reported in the input data set will be performed as follows for calculation of PK parameters:

- Pre-dose sample times will be entered as zero
- Values that are BLQ obtained prior to Cmax will be entered as zero
- Values that are BLQ after Cmax will be treated as missing but where BLQ concentrations are defined as parameters these will be reported as BLQ
- Values that are BLQ after Cmax may be imputed as zero for the calculation of partial AUCs, in cases where lambda-z cannot be determined
- Values that are measurable after at least 2 consecutive BLQ values after Cmax will be treated as missing for the calculation of PK parameters
- Values that are reported as "No Result" or "Not Reportable" (NR), "Not Calculated" (NC) or "No Sample" (NS) etc. will be generally be considered missing

Missing or unusual concentration values in the input data may be queried to ascertain any underlying cause. Exclusion of missing or unusual concentration values, or repeat bioanalysis of samples, will only be performed if a definitive root cause can be established and approval from Melinta Therapeutics has been obtained. Any exclusions of concentration values or repeat analysis of samples will be documented appropriately.

Plasma PK parameters will be estimated using standard Phoenix WinNonlin methods, details of which may be found in the documentation accompanying the WinNonlin software package. The rules specified in [Table 4](#) will be applied:

Table 4 PK Parameter Estimation Details

Sampling times	Actual
Calculation method	Linear trapezoidal linear interpolation
Number of points used for lambda-z	At least 3, not including Cmax
Minimum requirements for AUC	At least 3 consecutive measurable concentrations

Where possible, the terminal elimination rate constant (lambda-z) will be calculated for all subject profiles. The value of lambda-z will be determined by the slope of the

regression line of the natural log transformed concentrations vs time.

The WinNonlin-determined choice of data points for determination of lambda-z will be reviewed by the pharmacokineticist, who may adjust the selection in order to provide a more appropriate fit. The choice of data points for determination of lambda-z for each profile will be confirmed following a documented peer review.

9.1.3 Plasma PK Parameter Reporting Specifications

The following parameters will be reported for each regimen, as applicable, according to the rounding specifications provided in Table 1 and 2:

delafloxacin Tablet (reference)

Tlag, Tmax, Cmax, AUC(0-24), AUC(0-last), AUC(0-inf), AUCextrap, T1/2, lambda-z, CL/F, Vz/F, MRT(0-last), MRT(0-inf), lambda-z lower, lambda-z upper

delafloxacin Powder for Oral Suspension (test)

Tlag, Tmax, Cmax, AUC(0-24), AUC(0-last), AUC(0-inf), AUCextrap, T1/2, lambda-z, CL/F, Vz/F, MRT(0-last), MRT(0-inf), Frel Cmax^a, Frel AUC(0-last)^a, Frel AUC(0-inf)^a, lambda-z lower, lambda-z upper

^a Additional Frels based on Cmax, AUC(0-last), and AUC(0-inf) will be included, where possible, for the assessment of food effect.

The flags/footnotes given in [Table 5](#) will be applied to the PK parameters, where relevant, and will be shown in the PK parameter listings. Additional flags may be applied based on emerging data.

Table 5 PK Parameter Flags and Footnotes

Flag	Footnote
a	Adjusted R ² of regression (the goodness of fit statistic for the elimination phase) was <0.9
b	Period used for regression analysis was less than 2-fold the calculated half-life
c	Extrapolated portion of AUC(0-inf) >20%
d	Insufficient post-Cmax data points for estimation of lambda-z
e	Entire profile BLQ, no PK parameters could be calculated
f	Fewer than 3 consecutive measurable concentrations, AUCs not calculated
g	Measurable pre-dose values were observed, however were considered less than 5 % of Cmax

In the event that the adjusted R² of regression is <0.9 ("a" flag) then lambda-z and parameter estimates derived using lambda-z and AUC(0-inf) will be deemed unreliable and will be flagged and listed but excluded from the summary statistics and formal statistical analysis.

In the event that the time period used for regression analysis is less than 2-fold the calculated half-life ("b" flag) will be flagged, listed, and included in summary statistics and formal statistical analysis.

In the event that the extrapolated portion of AUC(0-inf) >20% ("c" flag), then AUC(0-inf) and parameter estimates derived using AUC(0-inf) will be deemed unreliable and will be flagged and listed but excluded from the summary statistics and formal statistical analysis.

In the event that there are insufficient post-Cmax data points for estimation of lambda-z ("d" flag) then lambda-z and parameter estimates derived using lambda-z and AUC(0-inf) will be reported as NC.

In the event that there are fewer than 3 consecutive measurable concentrations ("f" flag) then all AUC parameter estimates will be reported as NC.

In the event that measurable pre-dose values less than 5% of Cmax were observed ("g" flag), all parameter estimates for the profiles affected will be listed, flagged, and included in summary statistics and formal statistical analysis.

Note: in the event that measurable pre-dose concentrations greater than 5% of Cmax are observed, requirements for additional flags and further action will be agreed with Melinta Therapeutics and documented at the same time as the PK population.

9.2 Concentration and PK Summary Tables

Summary statistics (i.e., n, mean, SD, CV%, median, minimum, maximum, geometric mean, geometric SD, and geometric CV%) of concentration data will be calculated for each time point and regimen for delafloxacin in plasma. The number of BLQ values (n#) per time point will also be presented. Geometric statistics will not be calculated for Day 1, pre-dose concentrations.

Summary statistics (i.e., n, mean, SD, CV%, median, minimum, and maximum) of plasma PK parameters will be calculated for delafloxacin for each regimen. Geometric mean, geometric SD, and geometric CV% will be presented for all plasma PK parameters except Tlag and Tmax.

Non-measurable values reported in the plasma concentration data (i.e., values that are BLQ), will be entered as zero for the determination of summary statistics, with the exception of geometric means, geometric SD, and geometric CV%, where BLQ values will be imputed as half the lower limit of quantification (LLOQ) value. Data recorded as NR, NS, or NC will be handled as missing (i.e., no assumption will be made about the actual concentration).

9.3 Concentration and PK Figures

Mean, spaghetti, and individual plasma concentration vs time plots will be produced on both the linear/linear scale and \log_{10} /linear scale.

Mean plasma concentration vs time plots (using nominal times) will be produced for:

- All regimens given in the fasted state on the same plot (1 plot in total with up to 4 profiles per plot)
- Powder for Oral Suspension in the fed and fasted state for the food effect assessment on the same (1 plot in total with 2 profiles per plot).

These will be produced as follows:

- Linear/linear scale using arithmetic mean concentrations (error bars \pm arithmetic SD)
- \log_{10} /linear scale using geometric mean concentrations (error bars \times/\div geometric SD)

Separate plasma concentration vs time spaghetti plots (using actual sampling time after dosing) will be produced for each regimen with each plot displaying 1 line per subject.

Individual plasma concentration vs time plots (using actual sampling times after dosing) will be produced separately for each individual subject with all regimens on the same plot.

For all plots on a linear/linear scale, pre-dose concentration values reported as BLQ will be set to zero. Post-dose concentration values reported as BLQ will be set to zero, up to the point at which all concentrations fall below the LLOQ, after which they will be presented as missing. For all plots on a \log_{10} /linear scale, pre-dose concentration values reported as BLQ will be presented as missing. Post-dose concentration values reported as BLQ will be set to half the BLQ value, up to the point at which all concentrations fall below the LLOQ, after which they will be presented as missing. Where curves from multiple regimens or subjects are overlaid on the same plot, symbols will be used to identify different subjects/regimens and a legend will be included on the plots to define the symbols used.

9.4 Concentration and PK Listings

The sample collection data (e.g., collection times) for PK samples will be listed. In addition, all concentration data and PK parameters will be listed on a per subject basis. Any flags used will be included as a footnote with the appropriate definition. Both listings will be presented by all enrolled subjects.

9.5 Statistical Analysis of PK Parameters

For each analysis, distributional assumptions underlying the statistical analyses will be assessed by visual inspection of residual plots. Normality will be examined by normal probability plots, while homogeneity of variance will be assessed by plotting the residuals against the predicted values for the model. If the distributional assumptions for the parametric approach are not satisfied, then additional sensitivity analyses may be performed including the removal of potential outliers or the use of non-parametric methods to assess the robustness of the original analysis. This will be documented in the CSR together with the reasoning supporting the most appropriate action taken, if applicable. In general terms, the results of the original analysis will always be presented in the CSR.

9.5.1 Relative Bioavailability

Statistical analyses will be performed on the PK parameters Cmax, AUC(0-last), and AUC(0-inf). The parameters will undergo a natural logarithmic transformation and will be analysed using a mixed effects model. The model will include terms for regimen, period and sequence as fixed effects, and subject within sequence as a random effect.

The following comparison is of interest (test vs reference):

- Regimen B (delafloxacin Powder for Oral Suspension) vs Regimen A (delafloxacin Tablet [reference])

Subjects will be included in the analysis if they have data for both test and reference in regimens included in the comparison above.

The adjusted means, including differences from the pairwise comparisons and their associated 90% CIs obtained from the model, will be back transformed on the log scale to obtain adjusted geometric mean ratios (GMRs) and 90% CIs of the ratios.

The statistical analysis will be performed using actual regimen received and planned sequence, as detailed on the randomisation schedule. The model will be fitted using the SAS Software procedure PROC MIXED. The method will be specified as Restricted Maximum Likelihood and the denominator degrees of freedom for the fixed effects will be calculated using Kenward and Roger's method [4]. The following is an example of the SAS Software code that will be used:

```
PROC MIXED DATA= METHOD=REML ORDER=INTERNAL;
  CLASS TRTAN APERIODN TRTSEQPN;
  MODEL LVAR = TRTAN APERIODN TRTSEQPN / OUTP=PRED DDFM=KR;
  RANDOM SUBJIDN(TRTSEQPN);
  ESTIMATE <relevant pairwise treatment comparisons> / CL ALPHA=0.10;
  LSMEANS TRTAN / ALPHA=0.10;
  ODS OUTPUT LSMEANS=MEANS ESTIMATES=EST;
RUN;
```

where

- LVAR is the natural log transformed PK parameter of interest
- SUBJIDN is the numeric subject identifier variable
- TRTAN is the numeric treatment variable for the actual treatment received
- TRTSEQPN is the numeric sequence variable for the planned sequence received
- APERIODN is the numeric period variable

If there are any deviations from the planned treatment, then the analysis model specified or methods of analysis may be re-evaluated, as appropriate. Details of any deviations from the planned analysis will be documented in the CSR.

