9.5.2 Food Effect and Optional Dose Proportionality

Formal statistical analysis will be performed on the PK parameters Cmax, AUC(0-last), and AUC(0-inf) to assess the presence of food effect.

Additionally, formal statistical analysis will be performed on the dose-corrected PK parameters Cmax, AUC(0-last), and AUC(0-inf) to assess dose proportionality, if two dose levels of delafloxacin Powder for Oral Suspension are administered in the same prandial state.

For both food effect and dose proportionality analysis, the PK parameters will undergo a natural logarithmic transformation and will be analysed using a mixed effects model. The model will include terms for regimen as fixed effect and subject as a random effect.

The following comparisons are of interest:

- Regimen <C or D> (delafloxacin Powder for Oral Suspension Fed) vs Regimen B (delafloxacin Powder for Oral Suspension Fasted) (assessment of food effect)
- Regimen <C or D> (delafloxacin Powder for Oral Suspension yy mg) vs Regimen X (delafloxacin Powder for Oral Suspension xx mg) (where yy mg > xx mg) (optional assessment of dose proportionality)

For the assessment of food effect, subjects will be included in the analysis if they have data for both the fed and fasted state in regimens included in the comparison above.

The adjusted means, including differences from the comparisons and their associated 90% CIs obtained from the model, will be back transformed on the log scale to obtain adjusted GMRs and 90% CIs of the ratios.

The analysis will be performed using the SAS procedure PROC MIXED. The method will be specified as Restricted Maximum Likelihood and the denominator degrees of freedom for the fixed effects will be calculated using Kenward-Roger method [4]. The following is an example of the SAS Software code that will be used:

```
PROC MIXED DATA= METHOD=REML ORDER=INTERNAL;
  CLASS TRTAN;
  MODEL LVAR = TRTAN / OUTP=PRED DDFM=KR;
  RANDOM SUBJIDN;
  ESTIMATE <relevant pairwise treatment comparisons> / CL ALPHA=0.10;
  LSMEANS TRTAN / ALPHA=0.10;
  LSMEANS=MEANS ESTIMATES=EST;
RUN;
```

- where LVAR is the natural log transformed PK parameter of interest
- SUBJIDN is the numeric subject identifier variable
- TRTAN is the numeric treatment variable for the actual treatment (i.e., prandial state or Dose) received

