		all other p-values will be presented to 2 decimal places
Statistical analysis	i refers to the number of decimal places reported in the eCRF or other appropriate source data for the original data. Where bioanalytical or PK data are received rounded in significant figures rather than decimal places, summary statistics will be supplied to the same precision.	
	if <0.001: presented as <0.001	
	if ≥0.001 and <0.099: presented to 3 decimal places	
	all other p-values will be presented to 2 decimal places	

i refers to the number of decimal places reported in the eCRF or other appropriate source data for the original data. Where bioanalytical or PK data are received rounded in significant figures rather than decimal places, summary statistics will be supplied to the same precision.

* Where ratios are not presented as (%) (e.g., optional assessment of dose proportionality)

Details of how the individual PK parameters will be presented are detailed in [Section 9.1.1](#). Where data requires rounding, values ending with 1 to 4 will be rounded down and values ending with 5 to 9 will be rounded up.

All data listings will be based on all enrolled subjects (as defined in [Section 3.2.1](#)). Details of age and sex will be included on all data listings.

All statistical tests relating to PK parameters will be 2-sided and will be performed using a 10% significance level, leading to 90% (2-sided) confidence intervals (CIs).

If any baseline measurements are found to be missing then consideration will be given to imputation using the preceding time point (e.g., screening, admission, if applicable). Unscheduled assessment may be used if appropriate. Details of any such imputations will be documented as part of the safety analysis set.

There will be no other imputations for the safety data with regard to missing values or study discontinuation (i.e., subjects who do not complete the study). Imputation for PK parameter estimation using WinNonlin is described in [Section 9.1.2](#) and for reporting PK data is described in [Section 9.1.3](#).

If partial dates are available for smoking history, prior medications, or medical/surgical history, there will be no date imputations. The data listings will only show the date information for the date part that is available (e.g., if only the year part of the date is available then YYYY will be presented in the listing). If the full date information is missing, then this will be presented as missing on the data listing.

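### Both PROC MIXED examples omit the numeric subject ID from CLASS, so the printed code fits no subject effect and the 90% CIs lose the within-subject pairing

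*SAP*

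**What the plan says.** For the primary comparison (Regimen B against Regimen A), SAP 9.5.1 states: "The model will include terms for regimen, period and sequence as fixed effects, and subject within sequence as a random effect". It then gives PROC MIXED code, introduced with "The following is an example of the SAS Software code that will be used". The relevant lines are "CLASS TRTAN APERIODN TRTSEQPN" and "RANDOM SUBJIDN(TRTSEQPN" (closing bracket follows). The variable list adds: "SUBJIDN is the numeric subject identifier variable".

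For food effect and the optional dose-proportionality analysis, SAP 9.5.2 states: "The model will include terms for regimen as fixed effect and subject as a random effect". Its code puts only TRTAN in CLASS and then has "RANDOM SUBJIDN". SUBJIDN is again defined as numeric.

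Neither block has a SUBJECT= option or a REPEATED statement. The footnotes to mock Tables 14.2.3.1 and 14.2.3.2 repeat the description in the text, with subject nested within sequence as the random effect. SAP 14.1 sets the level: "All statistical tests relating to PK parameters will be 2-sided and will be performed using a 10% significance level", which gives 90% CIs. Protocol 15.4 says that no hypothesis is tested and that results are read from the geometric mean ratios and their 90% CIs.

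**The concern.** In PROC MIXED a numeric variable that is not in CLASS enters as a continuous covariate. The 9.5.1 RANDOM term then means one random slope on subject number for each sequence, and the 9.5.2 term means one random slope on subject number overall. Both are legal syntax, so the omission does not by itself stop the program. No subject-specific effect is separated from the residual, and the only correlation modelled is a shared trend in the ID number, which has no meaning here.

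The reason to run a crossover in 16 subjects is that each subject is his or her own control. The code as printed gives that up. It affects the interval for the primary endpoint (AUC, suspension against tablet), for the secondary food-effect endpoint and for dose proportionality. The residual plots in SAP 9.5, which can lead to sensitivity analyses with outliers removed or with non-parametric methods, would be drawn from residuals that still contain subject differences. The degrees of freedom and F-tests in Table 14.2.3.2 would come from the same wrong fit.

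**Working it through.** The plan states no CV, power or interval width, so there is no figure of its own to reproduce. The check compares the model described with the model coded.

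**Inputs from the documents.** 16 subjects planned and at least 12 evaluable (SAP 5.3); 8 per sequence (SAP 5.4); complete pairs only (SAP 9.5.1); two-sided 90% CI (SAP 14.1).

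**Assumed inputs.** Within-subject CV 15–30%, between-subject CV 20–40%, true ratio 100%.

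**Formulas, log scale.** Variance is s² = ln(1 + CV²).

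- Described (9.5.1): half-width = t(0.95, n − 2) × √(2·s²w/n)
- Coded, approximately: half-width = t(0.95, 2n − 4) × √(2·(s²w + s²b)/n)

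The second formula holds because, with complete pairs, the regimen contrast is orthogonal to the slope columns. Its error term is then the residual, which now carries the between-subject variance. The degrees of freedom are 2n records less four fixed-effect parameters.

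**Base case: within 20%, between 30%, n = 16.**

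- s²w = ln(1.04) = 0.0392; s²b = ln(1.09) = 0.0862
- Described: 1.761 × √(2 × 0.0392/16) = 1.761 × 0.0700 = 0.123, so 88.4–113.1%
- Coded: 1.701 × √(2 × 0.1254/16) = 1.701 × 0.1252 = 0.213, so 80.8–123.7%
- Width ratio: 0.213/0.123 = 1.73

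**Other settings (closed form; last column from simulation).**

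| n | CV between / within | Described | Coded | Ratio | Simulated ratio |
|---|---|---|---|---|---|
| 16 | 20% / 20% | 88.4–113.1 | 84.5–118.3 | 1.37 | 1.30–1.32 |
| 16 | 30% / 15% | 91.1–109.7 | 82.0–121.9 | 2.13 | 2.04–2.08 |
| 16 | 30% / 20% | 88.4–113.1 | 80.8–123.7 | 1.73 | 1.64–1.68 |
| 16 | 40% / 20% | 88.4–113.1 | 77.1–129.8 | 2.11 | 1.97–2.06 |
| 16 | 30% / 30% | 83.3–120.1 | 77.9–128.4 | 1.37 | 1.33–1.36 |
| 12 | 30% / 20% | 86.4–115.8 | 77.9–128.3 | 1.70 | 1.61–1.63 |

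The extremes of the assumed range are 1.15 (between 20%, within 30%, n = 12) and 2.67 (between 40%, within 15%, n = 16), both closed form.

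**Simulation.** Both models were fitted by REML to simulated complete data, 300 replicates per setting, with subject numbers starting at 1 or at 101. Residual degrees of freedom stood in for Kenward–Roger. In the base case:

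- the coded interval averaged 81.6–122.6% (IDs from 1) and 81.7–122.3% (IDs from 101), against 88.6–112.9% and 88.4–113.1% for the described model;
- coverage was 99.0% and 99.7% as coded, against 91.3% and 90.7% as described (nominal 90%);
- the ratio estimate was the same under both models to rounding error;
- the food-effect code gave width ratios of 1.73 and 1.68.

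In separate 300-replicate runs of the base case, the chance that the CI lies inside 80–125% fell from about 83% to 26–28%. SAS itself was not run; equivalent design matrices were used.

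**The case against.** The strongest reply is that the model is correctly specified in words, twice in the text and again in the mock-table footnotes, and that the code is labelled an example. It cannot run as printed: the dataset name and the ESTIMATE contents are placeholders, and the 9.5.2 block has lost the ODS OUTPUT keyword before its output list. SAP 14.2.4 requires an independent statistician to review code, log and output. Table 14.2.3.2 would show about 28 degrees of freedom for regimen where 14 are expected at n = 16. In a base-case simulation the slope variance was estimated as exactly zero in about 43% of datasets, which a reviewer might notice.

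The error is also conservative: with complete pairs it widens the interval and leaves the ratio unbiased, even with unequal sequences. Dose and prandial-state decisions use the interim parameters and Frel, not this model. No equivalence criterion is set; the 80–125% lines appear only in the footnote to mock Figure 14.2.4.1, and SAP 16 calls the mock outputs illustrative.

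All of this stands as fact. It limits the harm to the case where the CLASS lines are used as printed, and the 80–125% probability should be read only as an illustration. It does not remove the contradiction. This is the only code given for these analyses, both blocks make the same omission, and the review step calls for peer review, not independent reprogramming. Since no hypothesis is tested, the 90% CI is the plan's main statement of uncertainty, and an interval covering about 99% of the time is not the one promised.

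**Conclusion.** The concern holds: the code in SAP 9.5.1 and 9.5.2 contradicts the text and is wrong as written. It touches the primary analysis and should be corrected before the code is used. Run as printed, it would leave the ratio estimate unchanged with complete pairs and make the 90% CI about 1.7 times too wide on the log scale at assumed CVs of 20% within and 30% between subjects. The factor is 1.15 to 2.67 over the assumed range. The size depends on the ratio of between- to within-subject variance, which the documents do not give; the effect is negligible only if between-subject variance is close to zero. The reading of the code rests on standard PROC MIXED handling of a numeric variable outside CLASS.

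**What to change.** Add SUBJIDN to the CLASS statement in both blocks and leave the RANDOM statements as they are:

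- 9.5.1: `CLASS SUBJIDN TRTAN APERIODN TRTSEQPN;`
- 9.5.2: `CLASS SUBJIDN TRTAN;`

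Restore ODS OUTPUT before the output list in 9.5.2 at the same time. Add a check to the statistical QC that the denominator degrees of freedom for regimen are about n − 2 in 9.5.1 (14 at n = 16) and n − 1 in 9.5.2 (15 at n = 16). The cost is one word in each of two code blocks. There is no downside, because the code then matches the model that the SAP already describes.
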